9.4 STATISTICAL ANALYSES

9.4.1 GENERAL APPROACH

The statistical analysis will consist of two sub-analyses. First, a descriptive analysis will be performed, followed by an analysis to determine differences between the intervention and control groups. These analyses will be conducted using STATA/MP statistical software.

In the initial descriptive analysis, qualitative variables (e.g., sex, socioeconomic status) will be described using absolute and relative frequencies. Continuous variables (e.g., age, HbA1c, weight, BMI, blood pressure, cholesterol, HOMA-IR) will be described using mean and standard deviation for normally distributed variables, or median and interquartile range for variables with non-normal distributions. Normality of quantitative variables will first be assessed using the Kolmogorov-Smirnov test. Group comparability will be assessed using standardized mean differences (SMD), with $SMD < 0.10$ indicating negligible imbalance and $SMD \geq 0.20$ indicating meaningful imbalance. Formal hypothesis testing at baseline will not be routinely performed; if included, such p-values will be reported as descriptive only.

The primary efficacy analysis will use analysis of covariance (ANCOVA), with the 6-month value of the primary outcome as the dependent variable and the baseline value as a covariate. The model will include prespecified covariates: baseline outcome, age, sex, site (if applicable), and block/stratum used in randomization. The primary result will be the adjusted mean difference between intervention and control. Absolute risk reduction, relative risk reduction, and number needed to treat will also be calculated.

The secondary efficacy analysis will be a longitudinal analysis. The effect of the intervention in terms of T2DM reversal or remission (dichotomous variable) will be estimated using a mixed-effects model for repeated measures (MMRM) with a random intercept for participant and fixed effects for time, group, and group \times time interaction.

All statistical tests will be two-sided, with a significance level of $\alpha = 0.05$ considered statistically significant.

9.4.2 ANALYSIS OF THE PRIMARY ENDPOINT(S)

The primary endpoint is the change in glycated hemoglobin (HbA1c, %) from baseline to 6 months. HbA1c is measured as a continuous variable on an interval scale. The endpoint will be calculated as the absolute difference between baseline HbA1c and the value obtained at 6 months.

The primary analysis will be performed using analysis of covariance (ANCOVA) with treatment group (intervention vs. control) as the fixed factor, and baseline HbA1c as a covariate to improve precision. Additional prespecified covariates will include age, sex, study site, and randomization block, based on their potential clinical relevance and to ensure adjustment for any residual imbalance despite randomization. A secondary, confirmatory analysis will be conducted using a

mixed-effects model for repeated measures (MMRM), which includes all available timepoints (baseline, 3 months, and 6 months). This model accounts for within-subject correlation by specifying an unstructured covariance matrix.

Results will be presented as adjusted mean differences between groups with 95% confidence intervals and corresponding two-sided p-values. Least-squares means (LSMEANS) will be used to report group means adjusted for covariates.

The Intention-to-Treat (ITT) population will be the primary analytic set, including all randomized participants according to their allocated group. A Per-Protocol (PP) population, defined as participants with at least 70% adherence to the intervention, will be analyzed as a sensitivity approach.

Handling of Missing Data; for ANCOVA, missing data at 6 months will be addressed using multiple imputation under the missing-at-random (MAR) assumption. In MMRM, missing data are implicitly handled under MAR. Additional sensitivity analyses will explore the robustness of results to different missing-data mechanisms.

For ANCOVA, residuals will be checked for normality and homoscedasticity. If these assumptions are substantially violated, transformations or nonparametric methods will be considered. For MMRM, model fit will be evaluated and alternative covariance structures tested.

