1 SUMMARY OF THE PROTOCOL

1.1 SYNOPSIS

Title:	Lifestyle Intervention Clinical Trial for the Remission of Type 2 Diabetes Mellitus in Primary Care (CREDOenAP) [Ensayo clínico de intervención estilo de vida para la reversión de Diabetes Mellitus tipo 2 en Atención Primaria (CREDOenAP)]
Grant Number:	N/A
Study Description:	Intervention program with intensive lifestyle counseling, added to standard pharmacological treatment subsequently adjusted according to clinical needs and outcomes. The intervention will last 6 months and consists of biweekly in-person and telephone visits. Patients will follow a personalized dietary plan with carbohydrate restriction, based on the recommendations of the American Diabetes Association; engage in moderate and accessible physical activity; implement circadian rhythm regularization; and receive psychological counseling and support.
Objectives*:	
Primary objective:
 
To quantify the proportion of Type 2 Diabetes (T2DM) remission among participants without evidence of absolute insulinopenia enrolled in the lifestyle intervention program (CREDOenAP) at the end of the program (6 months).
 
Secondary objectives:
 
- To quantify the percentage of T2DM remission among participants in the lifestyle intervention program (CREDOenAP) one year after completion of the program (18 months).- To determine the nutritional, physical activity, and quality-of-life patterns of participants in the CREDOenAP program before, at the end of the intervention and one year after (18 months).- To assess anthropometric, metabolic, and imaging markers of cardiovascular risk in participants in the CREDOenAP program before, at the end of the intervention (6 months) and one year after completion (18 months).

Endpoints^{*}:

Primary Endpoint:

- Percentage of participants achieving type 2 diabetes remission at 6 months, defined as HbA1c <6.5% after 6 months of intervention and at least 3 months without antidiabetic medication. HbA1c will be determined through fasting blood analysis (minimum 8 hours).
- Percentage of participants achieving T2DM remission at 6 months, defined as fasting venous plasma glucose <126 mg/dL after 6 months of intervention and at least 3 months without antidiabetic medication. Fasting glucose will be measured through venous blood analysis after a minimum 8-hour fast.

Secondary Endpoints:

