3 OBJECTIVES AND ENDPOINTS

OBJECTIVES	ENDPOINTS	JUSTIFICATION FOR ENDPOINTS

Primary
 
To quantify the percentage of type 2 diabetes (T2DM) reversal among participants without signs of absolute insulinopenia enrolled in the CREDOenAP lifestyle intervention program at the end of the program (6 months).
	
Percentage of participants achieving type 2 diabetes (T2DM) remission at 6 months, defined as HbA1c <6.5% after 6 months of intervention and at least 3 months without antidiabetic medication. HbA1c will be measured from fasting venous blood samples (minimum 8 hours fasting).
 
Percentage of participants achieving T2DM remission at 6 months, defined as fasting venous plasma glucose <126 mg/dL after 6 months of intervention and at least 3 months without antidiabetic medication. Fasting plasma glucose will be measured from venous blood samples after a minimum 8-hour fast.
	
These measures allow evaluation of the intervention's efficacy, as they are widely accepted indicators of type 2 diabetes (T2DM) remission. These criteria have been consensually established and accepted by international organizations such as the American Diabetes Association (ADA) and the European Association for the Study of Diabetes (EASD).

Secondary		
1. To quantify the percentage of type 2 diabetes (T2DM) remission among participants in the CREDOenAP lifestyle intervention program one year after completing the program (18 months).	
Percentage of participants maintaining type 2 diabetes (T2DM) remission at 18 months, defined as HbA1c <6.5% after 12 months following the intervention and at least 9 months without antidiabetic medication.
 
Percentage of participants maintaining T2DM remission at 18 months, defined as fasting venous plasma glucose <126 mg/dL after 12 months following the intervention and at least 9 months without antidiabetic medication
	
These measures allow evaluation of the efficacy and long-term sustainability of the intervention, as they are widely accepted indicators of type 2 diabetes (T2DM) remission. These criteria have been consensually established and accepted by international organizations such as the American Diabetes Association (ADA) and the European Association for the Study of Diabetes (EASD).

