5.1 INCLUSION CRITERIA

The inclusion criteria for patient recruitment in this study are as follows:

1. Signed informed consent.
2. Men and women aged 18–80 years, inclusive.
3. Confirmed diagnosis of T2DM according to recognized diagnostic criteria (*Association, 2021*)
4. Most recent recorded hemoglobin A1c (HbA1c) > 6.5%.
5. Body Mass Index (BMI) greater than 27 kg/m².

Individuals considered eligible for recruitment must meet all of the above inclusion criteria and be able to comply with the activities described in the intervention process.

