8 STUDY ASSESSMENTS AND PROCEDURES

8.1 ENDPOINT AND OTHER NON-SAFETY ASSESSMENTS

To evaluate the effectiveness of the CREDOenAP intervention on the different health indicators defined in the objectives, various variables will be collected.

Sociodemographic Variables

- **Sex:** dichotomous variable according to biological sex (Male/Female).

- **Age:** age at study entry.
- **Living situation:** current living arrangement (Lives alone / Lives with others).
- **Socioeconomic level:** determined using the individual health insurance card (TSI) based on the pharmaceutical copayment level. Copayment is calculated according to each individual's income and employment status. Based on the copayment contribution, individuals are categorized into four socioeconomic levels:
 - **Very low:** TSI 001, exempt from copayment. Includes individuals receiving minimum insertion income, active insertion income, guaranteed citizen income, exhausted unemployment benefits, or non-contributory pensions.
 - **Low:** TSI 002 (10% copayment) and TSI 003 (40% copayment). Population with annual income < €18,000.
 - **Medium:** TSI 004 (50% copayment) and TSI 006. Population with annual income €18,000–€100,000 or individuals in administrative mutual schemes.
 - **High:** TSI 005 (60% copayment). Population with annual income > €100,000.

Clinical Variables

- **Year of T2DM diagnosis:** year of T2DM registration in eCAP.
- **Main comorbidities:** the primary active diagnoses recorded in eCAP will be obtained and corroborated with the participant.

Primary Outcome Variables

All primary outcome variables will be measured, calculated, and recorded at study baseline, at the end of the intervention, and 12 months after the intervention.

- **Presence of T2DM remission** (according to ADA consensus definition, (Riddle *et al.*, 2021)):
 - **Glycated hemoglobin (HbA1c):** T2DM remission will be considered if HbA1c is < 6.5% after 6 months of intervention and at least 3 months without antidiabetic medication. HbA1c will be determined by blood analysis after a minimum of 8 hours of fasting (Association, 2021)
 - **Fasting plasma glucose:** T2DM remission will be considered if fasting venous plasma glucose is < 126 mg/dL after 6 months of intervention and at least 3 months without antidiabetic medication. Fasting plasma glucose will be measured by venous blood analysis after a minimum of 8 hours of fasting (Association, 2021)

Secondary Outcome Variables

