9 STATISTICAL CONSIDERATIONS

9.1 STATISTICAL HYPOTHESES

Primary Endpoint:

The primary hypothesis is based on the null hypothesis (H_0), which states that there is no difference in the percentage of type 2 diabetes (T2DM) remission between the intervention group and the control group. Conversely, the alternative hypothesis (H_1) states that the percentage of T2DM remission will be significantly higher in the intervention group compared to the control group. An efficacy analysis is planned and will be evaluated right after the end of the intervention.

Secondary Endpoints:

The null hypothesis (H_0) states that there will be no significant differences in the proposed secondary variables (metabolic, behavioral, and quality-of-life variables) between the intervention group and the control group. Conversely, the alternative hypothesis (H_1) states that there will be statistically significant differences in the proposed secondary variables (metabolic, behavioral, and quality-of-life variables), with more favorable outcomes for the intervention group compared to the control group. An efficacy analysis of the intervention is planned, and the evaluation will be carried out 12 months after the end of the intervention.

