9.2 SAMPLE SIZE DETERMINATION

Based on the primary variable of the intervention, the percentage of T2DM remission, the required sample size has been calculated to observe statistically significant differences. This variable will be coded dichotomously. A total of 120 volunteers (60 per arm) will be recruited for the study. Accepting an alpha risk of 0.05 (5%) and a beta risk of less than 0.2 in a two-sided test, at least 52 subjects in the control group and 52 subjects in the intervention group would be required to detect as statistically significant a 20% difference between two proportions (primary endpoint: T2DM remission). For the control group, the expected remission rate ranges from 0 to 5%, whereas in the intervention group, it is expected to be at least 25%. The remission rates have been benchmarked against previous studies (Lean et al., n.d.). An estimated loss to follow-up rate of 15% has been considered.

Given the estimated 15% loss to follow-up, the sample size has been increased to 60 participants instead of 52. This ensures that the statistical power of the analysis will be preserved.

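### Section 9.4.2 makes change in HbA1c the primary test, while the objectives, hypothesis and sample size make 6-month remission primary

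*Protocol*

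**What the plan says.** Five places make remission at 6 months primary.

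- The Synopsis gives "Percentage of participants achieving type 2 diabetes remission at 6 months, defined as HbA1c <6.5% after 6 months of intervention", with a drug-free period of at least 3 months. Section 3 repeats this and adds a second version: "Percentage of participants achieving T2DM remission at 6 months, defined as fasting venous plasma glucose <126 mg/dL after 6 months of intervention", with the same drug-free condition.
- Section 8.1, under the primary outcome variables: "T2DM remission will be considered if HbA1c is < 6.5% after 6 months of intervention and at least 3 months without antidiabetic medication".
- Section 9.1, null hypothesis: "there is no difference in the percentage of type 2 diabetes (T2DM) remission between the intervention group and the control group".
- Section 9.2: "Based on the primary variable of the intervention, the percentage of T2DM remission, the required sample size has been calculated". The variable is dichotomous, with 0 to 5% expected under control and at least 25% under intervention.

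Section 9.4 departs from this. Section 9.4.2 opens with "The primary endpoint is the change in glycated hemoglobin (HbA1c, %) from baseline to 6 months" and assigns ANCOVA. Section 9.4.1 says "The primary result will be the adjusted mean difference between intervention and control". HbA1c change is not listed as an endpoint at any level in the Synopsis or Section 3.

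Remission does appear in the analysis sections, but with lower rank or without a test. Section 9.4.1 has a longitudinal model labelled secondary, and adds risk reductions and a number needed to treat without naming the outcome. Section 9.4.3 has a mixed logistic model for remission at 18 months, and a logistic regression for reaching HbA1c below 6.5% with no drug-free condition.

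**The concern.** If Section 9.4.2 is followed, the primary p-value does not test the hypothesis in Section 9.1, and the power in Section 9.2 does not describe it.

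The two endpoints are not interchangeable. Remission requires a drug-free period; HbA1c change does not. Drug treatment can move in either direction during the trial: the Synopsis has it adjusted to clinical need, and Section 6.5.1 allows drugs to be started. HbA1c can therefore fall on medication without remission, and the trial could be called positive without showing its stated objective. Conversely, stopping drugs can narrow the HbA1c gap between arms while remission rises.

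The trial is open-label. With two candidate primary endpoints in the text, the one that decides could be chosen after the results are seen.

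**Working it through.** **1. Where the sample size comes from.** Inputs from Section 9.2: control 5% (upper end of 0 to 5%), intervention 25%, two-sided alpha 0.05, power at least 80%, 1:1 allocation; stated result 52 per arm.

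Pooled variance in both terms, mean rate 0.15:

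n = 2 × (1.960 + 0.842)² × 0.15 × 0.85 / 0.20² = 50.04, so 51 per arm.

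The usual formula (pooled under the null, unpooled under the alternative) gives 49. A control rate of 2.5% against 22.5% with continuity correction gives exactly 52. The stated 52 is therefore a two-proportion figure for remission. Its inflation is 52 × 1.15 = 59.8, so 60; after 15% loss, 60 × 0.85 = 51 remain, one below the stated minimum.

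**2. Power for remission, 5% versus 25%.** Power = Φ[(0.20 − 1.96 × SE0) / SE1], where SE0 = √(2 × 0.15 × 0.85 / n) and SE1 = √((0.05 × 0.95 + 0.25 × 0.75) / n).

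At n = 51: SE0 = 0.0707, SE1 = 0.0679, so Φ[(0.20 − 0.1386) / 0.0679] = Φ(0.905) = 81.7%.

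| Per arm | Pooled z-test | Fisher's exact test |
|---|---|---|
| 51 | 81.7% | 76.1% |
| 52 | 82.5% | 77.2% |
| 60 | 87.6% | 84.5% |

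**3. Power for HbA1c change.** The protocol gives no target difference and no standard deviation, so this cannot be computed from it. The figures below are assumptions, used only to show how widely the answer varies. They use a two-sample t-test with 51 per arm and noncentrality (gap / residual SD) × √(51/2), where residual SD = SD × √(1 − r²) and r is the correlation with baseline.

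| Gap (HbA1c points) | SD 1.0, r = 0 | Range: SD 0.8 to 1.5, r 0 to 0.5 |
|---|---|---|
| 0.18 | 15% | 9 to 26% |
| 0.40 | 52% | 27 to 82% |
| 0.56 | 80% | 46 to 98% |

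The gap needed for 80% power runs from 0.39 points (SD 0.8, r = 0.5) to 0.84 points (SD 1.5, r = 0).

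**4. Can Section 9.4.1 be read as an analysis of remission?** It regresses the 6-month value of the primary outcome on its baseline value. Entry requires "Most recent recorded hemoglobin A1c (HbA1c) > 6.5"%, so by the HbA1c definition almost nobody is in remission at baseline. The covariate would be nearly constant, and an adjusted mean difference is not how a yes/no outcome is normally reported. Section 9.4.2 closes off this reading in any case by naming HbA1c as a continuous variable.

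**The case against.** The contradiction itself is hard to dispute. The fair objections concern its weight and the remedy.

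- *Remission is not absent.* The risk reductions and number needed to treat stand in the same paragraph as the primary analysis and make sense only for a binary outcome, and the group-by-time model could yield a 6-month contrast. That is correct. What is missing is a primary test of 6-month remission as defined.
- *The HbA1c test is not shown to be underpowered.* Also correct. The ranges above are too wide to support that, and the point here is only that the stated power belongs to a different test.
- *Keeping HbA1c change as primary would also be coherent.* It would, if the objectives, hypothesis and sample size were rewritten around a justified difference and standard deviation. That changes more of the protocol and moves it away from its stated purpose.
- *A binary analysis has its own difficulties.* This stands as a caution. With 51 controls, the chance of no control remissions is 0.95^51 = 7% at a 5% rate and 0.975^51 = 27% at 2.5%. Ordinary logistic regression can fail there, and the four binary stratification factors form 16 cells. Fisher's exact test falls below 80% power at 51 per arm.
- *The analysis set is unsettled.* Section 9.3 restricts intention-to-treat to participants with data at all three time points, whereas Section 9.4.2 includes everyone randomised. That is a separate conflict, but it must be settled together with this one.

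**Conclusion.** The concern holds and should be fixed before any outcome data are examined. The protocol fixes two different primary endpoints, and the one attached to the primary test is neither the one in the hypothesis nor the one the trial was sized for. No other section resolves this, and because it is a conflict within the protocol it is not a detail that can be left to a statistical analysis plan.

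In size: the test the trial was planned around has about 82% power at 51 per arm and 88% at 60, assuming 5% versus 25% and a pooled z-test. The test named in Section 9.4.2 has no stated power and none that can be derived. The conclusion that the endpoints conflict does not depend on any assumed HbA1c figure.

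**What to change.** In Sections 9.4.1 and 9.4.2, name remission at 6 months, including the drug-free condition, as the single primary endpoint. State which of the two Section 3 definitions decides and make the other secondary; the HbA1c version is the one Section 9.4.3 already uses.

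Analyse it by allocated group in all randomised participants, as Section 9.4.2 says, and align Section 9.3 with that. Use a binary method adjusted for the stratification factors. A stratified risk difference is the safer choice at a control rate of 0 to 5%; if a logistic model with a standardised risk difference is preferred, name a fallback for zero control events. Report the 95% confidence interval and number needed to treat. Keep the multiple imputation planned for missing 6-month outcomes.

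Move HbA1c change by ANCOVA to the secondary endpoints and report it alongside medication use.

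The cost is wording. The 60 per arm can stand for a test that performs like the pooled z-test; an exact test would need the size reconsidered. No visits are added, but the schedule in Section 1.3 marks medication review at baseline and 18 months only, while Section 6.5 records medication at every visit. These should be aligned so that the drug-free period can be established at 6 months. The price of the change is that a binary outcome uses less information per participant than a continuous one.

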9.4.3 ANALYSIS OF THE SECONDARY ENDPOINT(S)

The secondary endpoint is diabetes remission at 18 months, defined as achieving HbA1c <6.5% without glucose-lowering medications. It will be analyzed using a generalized linear mixed-effects model (GLMM) with a logit link, including treatment group, time, and group \times time interaction as fixed effects, and a random intercept for participants to account for repeated measurements. Prespecified covariates include baseline HbA1c, age, sex, site, and randomization block. Results will be reported as adjusted odds ratios with 95% confidence intervals and two-sided p-values.

The analysis will follow the Intention-to-Treat (ITT) principle; a Per-Protocol (PP) analysis (adherence $\geq 70\%$) will be performed as sensitivity. Missing data will be handled under the missing-at-random assumption, with multiple imputation applied if necessary. Trajectories of remission probabilities over time will also be presented.

Others secondary endpoints include:

- Change in body weight (kg) from baseline to 6 months (continuous, interval scale).
- Change in blood pressure (systolic and diastolic, mmHg) from baseline to 6 months (continuous, interval scale).
- Change in lipid profile (total cholesterol, LDL-C, HDL-C, triglycerides, mg/dL) from baseline to 6 months (continuous, interval scale).
- Change in circadian rhythm regularity (measured via validated questionnaire scores; ordinal/interval scale).

- Change in health-related quality of life (measured via validated scale, e.g., SF-12 or equivalent; interval scale).
- Intervention adherence (measured as percentage of scheduled sessions completed; continuous, but categorized as adherent $\geq 70\%$ vs. non-adherent for analysis).

The analysis models for continuous outcomes (e.g., weight, blood pressure, lipid levels, quality of life scores) will be analyzed using ANCOVA with treatment group as a fixed factor and baseline values as covariates. Repeated measures across timepoints (baseline, 3 months, 6 months) will be analyzed with MMRM to account for within-participant correlations.

For binary/categorical outcomes (e.g., adherence $\geq 70\%$, achievement of HbA1c $< 6.5\%$) will be analyzed using logistic regression, adjusted for prespecified covariates.

For ordinal outcomes (e.g., circadian rhythm scores if treated as ordinal), ordinal logistic regression will be considered.

All analyses will adjust for baseline values of each outcome, plus prespecified covariates such as age, sex, and site. Covariate selection will be guided by clinical relevance and baseline comparability, aiming for a parsimonious model.

Results will be reported as adjusted mean changes with standard errors (for continuous outcomes), odds ratios with 95% confidence intervals (for binary/ordinal outcomes), and associated p-values. For binary endpoints, absolute risk differences and numbers-needed-to-treat (NNT) will also be reported when applicable.

The same approach as for the primary endpoint will be applied: MMRM for repeated measures (implicitly handling missing values under MAR) and multiple imputation for single-timepoint ANCOVA analyses. Sensitivity analyses will evaluate the robustness of results.

Normality and homoscedasticity will be checked for continuous outcomes. Logistic regression models will be checked for linearity in the logit and absence of multicollinearity. Ordinal models will be checked for proportional odds assumption.

